### **7.1.4 Discontinuation of study treatment**

Patients may voluntarily discontinue from the study treatment for any reason at any time. If a patient decides to discontinue from the study treatment, the investigator should make a reasonable effort (e.g. telephone, e-mail, letter) to understand the primary reason for this decision and record this information in the patient's chart and on the appropriate CRF pages. They may be considered withdrawn if they state an intention to withdraw, fail to return for visits, or become lost to follow-up for any other reason.

The investigator should discontinue study treatment for a given patient, if he/she believes that continuation would be detrimental to the patient's well-being.

Study treatment must be discontinued under the following circumstances:

- Emergence of specific adverse events or laboratory abnormalities under some circumstances as outlined in [Section 6](#).
- Use of prohibited treatment (refer to [Section 6.4.1](#))
- Any protocol deviation that results in a significant risk to the patient's safety

The appropriate personnel from the site and Novartis will assess whether study treatment should be discontinued for any patient whose treatment code has been broken inadvertently for any reason.

Patients who discontinue study treatment should NOT be considered withdrawn from the study. They should return for the assessments indicated in [Section 7.2.1](#). If they fail to return

for these assessments for unknown reasons, every effort (e.g. telephone, email, or letter) should be made to contact them as specified in [Section 7.1.7](#).

Patients who discontinue study treatment should undergo an end of treatment visit.

For patients who discontinue treatment for reasons other than documented disease progression, death, lost to follow-up, or withdrawal of consent, tumor assessments must continue to be performed per assessment schedule until documented disease, death, lost to follow-up, or withdrawal of consent.

The investigator must also contact the IRT to register the patient's discontinuation from study treatment within 2 days.

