#### **7.1.5 Withdrawal of consent**

Patients may voluntarily withdraw consent to participate in the study for any reason at any time. Withdrawal of consent occurs only when a patient does not want to participate in the study any longer, and does not want any further visits or assessments, and does not want any further study related contact.

Novartis will continue to retain and use all research results that have already been collected for the study evaluation. All biological samples that have already been collected may be retained and analyzed at a later date (or as required by local regulations).

If a patient withdraws consent, the investigator should make a reasonable effort (e.g. telephone, e-mail, letter) to understand the primary reason for this decision and record this information.

Study treatment must be discontinued and no further assessments conducted.

Further attempts to contact the patient are not allowed unless safety findings require communication or follow up.

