### **7.1.6.3 Survival follow-up**

All patients will be followed for survival status at least every 3 months after randomized treatment phase or post-treatment follow-up phase, unless they discontinued due to death, consent withdrawal or lost to follow-up. Survival information can be obtained via phone and information will be documented in the source documents and eCRF. Additional survival assessments may be performed more frequently if a survival update is required for reporting the results or to meet safety or regulatory requirements.

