### **7.1.7 Lost to follow-up**

For patients whose status is unclear because they fail to appear for study visits without stating an intention to withdraw consent, the investigator should show "due diligence" by contacting the patient, family or family physician as agreed in the informed consent and by documenting in the source documents steps taken to contact the patient, e.g. dates of telephone calls, registered letters, etc. A patient should not be considered lost to follow-up until due diligence has been completed. Patients lost to follow up should be recorded as such on the appropriate Disposition CRF.

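### Protocol 7.1.4 allows a patient who merely misses visits to be classed as withdrawn, contradicting its own later text and Sections 7.1.5 and 7.1.7, so follow-up can be closed early or under the wrong category

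*Protocol*

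**What the plan says.** The first paragraph of Protocol 7.1.4 concerns patients who decide to stop study treatment. It ends: "They may be considered withdrawn if they state an intention to withdraw, fail to return for visits, or become lost to follow-up". The three triggers are alternatives, so any one is sufficient.

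Further down, the same section says the opposite: "Patients who discontinue study treatment should NOT be considered withdrawn from the study". On patients who then do not come back, its wording is: "for these assessments for unknown reasons, every effort (e.g. telephone, email, or letter) should be made to contact them as specified in". The reference there is to 7.1.7.

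Section 7.1.5 defines the explicit act: "Withdrawal of consent occurs only when a patient does not want to participate in the study any longer", and she must also want no more visits, assessments or study contact. The protocol glossary repeats this definition. The consequences are strict. On treatment and assessments the rule is: "Study treatment must be discontinued and no further assessments conducted". On later contact by the site it is: "Further attempts to contact the patient are not allowed unless safety findings require communication or follow up".

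Section 7.1.7 covers patients who stop appearing without saying that they wish to withdraw consent. The site must try to reach the patient, her family or her physician and document each step: "A patient should not be considered lost to follow-up until due diligence has been completed". The record is then lost to follow-up.

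Survival follow-up under 7.1.6.3 applies to all patients "unless they discontinued due to death, consent withdrawal or lost to follow-up", and status can be obtained by telephone. Section 7.1.6.2 ends post-treatment scans on those same grounds and on progression.

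**The concern.** Two rules in force give different instructions for the same patient. A site that reads only the first paragraph of 7.1.4 can close a non-attender as withdrawn on the strength of missed visits. A site that reads on must try to contact her first and, if that fails, record her as lost.

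The difference matters because patients who stop coming may well have progressed, died or had toxicity. If contact attempts are skipped, or the patient is recorded as having withdrawn consent when she has not, scans and survival status that due diligence might have recovered are not sought. PFS is then censored at the last adequate tumor assessment and OS at the last contact date, possibly for reasons related to outcome. PFS is the primary endpoint, and the SAP plans a single OS analysis at the end of the study.

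**Working it through.** The point is settled mainly by setting the provisions side by side for one patient: she has stopped study treatment, misses her next visits, and has said nothing about withdrawing.

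| Provision | Required before a status is assigned | Resulting status |
|---|---|---|
| 7.1.4, first paragraph | Nothing beyond missed visits | Withdrawn (not defined there) |
| 7.1.4, later text | Every effort to contact, under 7.1.7 | Not withdrawn from the study |
| 7.1.5 and glossary | An expressed wish for no participation, visits, assessments or contact | Consent not withdrawn |
| 7.1.7 | Completed due diligence | Lost to follow-up |

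The first row conflicts with each of the others.

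**What the word triggers.** The bar on contact and assessments in 7.1.5 depends on withdrawal of consent. The stop rules in 7.1.6.2 and 7.1.6.3 list consent withdrawal and loss to follow-up. None lists plain withdrawn status. Follow-up is therefore lost early only if the site goes a step further: it stops pursuing the patient on the basis of 7.1.4, records loss to follow-up without due diligence, or records consent withdrawal that did not occur. The first paragraph permits the early closure; it does not require the later steps.

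**What the analysis then does.** SAP 2.5.3 censors PFS at the last adequate tumor assessment. SAP 2.7 censors OS at the last contact date. SAP 2.5.4 plans no sensitivity analysis for the final report. Nothing planned there would show the effect of such closures.

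**Planning figures (Protocol 10.6).**

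1. Interval. With 110 events, 1:1 allocation and 90% confidence, the half-width on the log scale is 1.645 × 2/√110 = 0.3137. Then 0.62 × exp(∓0.3137) = 0.453 and 0.848. The plan states 0.45 and 0.85, so it reproduces.
2. Events at month 22. With exponential PFS, 18 months of uniform accrual and λ = ln 2/median, the event probability is p = 1 − [exp(−4λ) − exp(−22λ)]/(18λ). Medians of 4.1 and 4.1/0.62 = 6.61 months give p = 0.841 and 0.704, mean 0.7726. Removing the planned 10% loss (160 × 0.10 = 16 patients), 144 × 0.7726 = 111.3 events. The number needed for 110 events is 110/(0.90 × 0.7726) = 158.2, consistent with about 160.
3. More loss than planned. The documents give no rate of premature closure, so these totals are assumptions only. If total loss were 15%, 20%, 25% or 30%, events at month 22 would be 105, 99, 93 or 87, and 110 events would come at about month 23.4, 25.8, 30.1 or 43.4.

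Because the analysis waits for about 110 events, extra loss delays it and does not widen the interval for a given observed hazard ratio. Any harm would be bias, which these calculations do not measure.

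**The case against.** The strongest reply is that the sentence is loose but harmless. Section 7.1.4 is headed as discontinuation of study treatment, and withdrawn has no object there, so it could mean withdrawn from treatment. The later text corrects it in capitals. The recording lists leave little room for error: the reasons for ending treatment in 6.1.5 and the PFS censoring reasons in Appendix 14.1.4.5.6 each separate loss to follow-up from withdrawal of consent, and Appendix 14.1.4.2 and 14.1.4.3 list loss to follow-up apart from patient decision. None offers withdrawal for non-attendance.

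The treatment-only reading is possible but weak. The paragraph already concerns patients who have decided to stop treatment, so on that reading the sentence adds little, and missed visits and loss to follow-up are matters of study participation. Section 7.1.6.1 blurs the terms again by asking, in its text on patients lost to follow-up, for the reason for premature withdrawal from the study. What stands is that the later text and the separate categories lower the practical risk. They do not remove the contradiction.

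A reader might infer that applying the 7.1.4 sentence automatically brings in the contact ban of 7.1.5 and the survival exemption of 7.1.6.3. The documents do not support that: neither is triggered by plain withdrawn status, and reaching the ban means disregarding the restrictive definition in 7.1.5 as well.

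It is also fair to say that a non-attender leaves survival follow-up once due diligence is complete, whichever paragraph is used. What is at stake is the contact that should happen before that point, and the category recorded.

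Finally, an amendment now would have little effect on conduct. The SAP records the primary cut-off (19 May 2020) and approval in China (9 February 2022), and approval for this indication is an end-of-study criterion. That is why the fix includes a check of records.

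**Conclusion.** The first paragraph of 7.1.4 is wrong as written. It contradicts the rest of its own section, the definition in 7.1.5 and the procedure in 7.1.7, and it permits a non-attender to be closed early, without contact attempts or under the wrong category. The possible result is informative censoring of PFS and missed deaths for OS.

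The size cannot be computed from the documents. It depends on how many sites relied on the sentence and on how many of those patients could have been traced; neither is given. A reader might try to size it as a share of the 16 patients expected to be lost. That would not be sound: the share has no source, those patients are already allowed for in the sample size, and not all would have had an event. Only patients whom due diligence would have recovered add to the planned loss.

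No sample-size error follows, and the width of the 90% interval at 110 events is unaffected. The remaining risk is bias in the estimates, of unknown size and direction.

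**What to change.** In 7.1.4, delete the second and third triggers of the sentence (non-attendance and loss to follow-up for any other reason). Limit withdrawn status to the explicit withdrawal of consent in 7.1.5. Refer non-attenders to 7.1.7, stating that contact and survival-status attempts continue until due diligence is complete. They should not be required beyond that point under this change, because that would alter the separate loss-to-follow-up exemption in 7.1.6.3.

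Because the primary cut-off has passed, the useful step now is a records check. Before the final analysis, compare each disposition record coded as withdrawal with the 7.1.5 definition. Where only non-attendance is documented, correct the category and confirm whether the 7.1.7 steps were carried out. Report the number of records changed.

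The cost is one sentence in an amendment or site memo and a review of the disposition records of at most about 160 patients. No change to the sample size or analysis model is needed.

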#### **7.1.4.1 Replacement policy**

Not applicable.

#### **7.1.5 Withdrawal of consent**

Patients may voluntarily withdraw consent to participate in the study for any reason at any time. Withdrawal of consent occurs only when a patient does not want to participate in the study any longer, and does not want any further visits or assessments, and does not want any further study related contact.

Novartis will continue to retain and use all research results that have already been collected for the study evaluation. All biological samples that have already been collected may be retained and analyzed at a later date (or as required by local regulations).

If a patient withdraws consent, the investigator should make a reasonable effort (e.g. telephone, e-mail, letter) to understand the primary reason for this decision and record this information.

Study treatment must be discontinued and no further assessments conducted.

Further attempts to contact the patient are not allowed unless safety findings require communication or follow up.

#### **7.1.6 Follow-up period**

##### **7.1.6.1 Follow up for safety evaluations**

All patients must have safety evaluations for 30 days after the last dose of study treatment. Adverse events and SAE information will be collected and recorded in the appropriate eCRFs. Record all concomitant medications or therapies used/taken to treat the SAEs.

Antineoplastic therapy regimen received between EOT and progression will also be collected as well as the first regimen received after progression.

For patients who are lost to follow-up, the investigator should show "due diligence" by documenting in the source documents steps taken to contact the patient, e.g., dates of telephone calls, registered letters, etc. The investigator must determine the primary reason for a patient's premature withdrawal from the study and record this information on the appropriate disposition CRF.

### **7.1.6.2 Post-treatment follow-up**

All patients who discontinued treatment during the treatment phase for reasons other than death, consent withdrawal, lost to follow-up or disease progression as per investigator assessment ([Section 7.1.3](#)) will continue tumor assessments as per [Table 7-1](#) thereafter until PD as per investigator assessment, withdrawal of consent or death. Once the patient ceases tumor follow-up, the reason for completion should be recorded on the End of Post Treatment Disposition eCRF page.

### **7.1.6.3 Survival follow-up**

All patients will be followed for survival status at least every 3 months after randomized treatment phase or post-treatment follow-up phase, unless they discontinued due to death, consent withdrawal or lost to follow-up. Survival information can be obtained via phone and information will be documented in the source documents and eCRF. Additional survival assessments may be performed more frequently if a survival update is required for reporting the results or to meet safety or regulatory requirements.

### **7.1.7 Lost to follow-up**

For patients whose status is unclear because they fail to appear for study visits without stating an intention to withdraw consent, the investigator should show "due diligence" by contacting the patient, family or family physician as agreed in the informed consent and by documenting in the source documents steps taken to contact the patient, e.g. dates of telephone calls, registered letters, etc. A patient should not be considered lost to follow-up until due diligence has been completed. Patients lost to follow up should be recorded as such on the appropriate Disposition CRF.

## **7.2 Assessment types**

### **7.2.1 Efficacy assessments**

#### **Efficacy assessments**

Tumor response will be assessed locally and centrally according to the Novartis guideline version 3.2 ([Appendix 1](#)) based on RECIST 1.1 ([Eisenhauer et al 2009](#)). The imaging assessment collection plan is presented in [Table 7-2](#). Details of the central review process will be described in the independent review charter.

Imaging data will be centrally collected and checked for quality by an imaging Contract Research Organization (CRO) designated by Novartis. Central review should stop after the number of events is reached for the primary PFS analysis. The results of the local investigator's assessment will be used for primary analysis purposes.

**Table 7-2 Imaging assessment collection plan**

Procedure	Screening/Baseline	During Treatment/Follow-up
Chest, abdomen and pelvis CT or MRI (with intravenous contrast enhancement)	Mandated	Mandated, every 8 weeks after randomization date until PD ( $\pm 7$ days); the assessment will be performed very 12 weeks after primary analysis data cut-off or as clinically indicated, until PD ( $\pm 7$ days)
Brain CT or MRI	Mandated	Mandated if lesions were documented at baseline, follow same schedule as CT/MRI of chest, abdomen, and pelvis
Whole body bone scan	Mandated	If clinically indicated
Localized bone CT, MRI or x-ray	For any lesions identified on the whole body bone scan that are not visible on the chest, abdomen and pelvis CT or MRI	Mandated if lesions were documented at baseline, follow same schedule as CT/MRI of chest, abdomen, and pelvis
Color photography (with scale/ruler)	For any skin lesions present	Mandated if lesions were documented at baseline, follow same schedule as CT/MRI of chest, abdomen, and pelvis
CT or MRI of other metastatic sites (e.g., neck)	If clinically indicated	Mandated if lesions were documented at baseline, follow same schedule as CT/MRI of chest, abdomen, and pelvis

### Baseline imaging assessments

Imaging assessments will be performed at screening/baseline within 21 days before start of treatment.

Any imaging assessments already completed during the regular work-up of the patient within 21 days prior to start of treatment, including before signing the main study ICF, can be considered as the baseline images for this study. Any imaging assessments obtained after randomization cannot be considered baseline images. The following assessments are required at screening/baseline:

- Chest, abdomen and pelvis CT or MRI
- Brain CT or MRI
- Whole body bone scan
- Localized bone CT, MRI or x-ray, for any lesions identified on the whole body bone scan that are not visible on the chest, abdomen and pelvis CT or MRI
- Color photography for any skin lesions present
- CT or MRI of other metastatic sites (e.g., neck), if clinically indicated

If a patient is known to have a contraindication to CT intravenous (IV) contrast media or develops a contraindication during the trial, a non-contrast CT of the chest (MRI is not recommended due to respiratory artifacts, however if CT is not feasible per local regulations, MRI can be performed instead) plus a contrast-enhanced MRI (if possible) of the abdomen and pelvis should be performed.

If brain metastases are suspected at baseline, brain MRI or CT should be completed. Contrast enhanced brain MRI is preferred, however, if MRI contrast is contraindicated, then MRI without contrast or CT with/without contrast is acceptable.

A whole body bone scan should be performed per institutional standard of care [e.g., Tc-99 bone scan, whole body bone MRI, Fluorodeoxyglucose positron emission tomography (FDG-PET) or sodium fluoride (NaF) PET]. After screening, whole body bone scans is not required, unless clinically indicated. If indicated, the same methodology as at screening should be used.

Localized CT, MRI or X-rays should be acquired for all skeletal lesions identified on the screening whole body bone scan, which are not visible on the chest, abdomen and pelvis CT/MRI. If skeletal lesions are documented at baseline, scans need to be continued following the same schedule as CT/MRI of chest, abdomen and pelvis. The same methodology as at screening should be used.

If clinically indicated, CT or MRI of other areas (e.g., neck) of disease as appropriate should be performed.

If skin lesions are present at screening, color photography should be acquired using a digital camera in clear focus, including a scale/ruler, in such a way that the size of the lesion(s) can be determined from the photograph.

Any potentially measurable lesion that has been previously treated with radiotherapy should be considered as a non-measurable lesion. However, if a lesion previously treated with radiotherapy has clearly progressed since the radiotherapy, it can be considered as a measurable lesion.

Chest x-rays and ultrasound should not be used to measure tumor lesions.

### **Post-baseline imaging assessments**

Imaging assessments as described in [Table 7-2](#) should be performed at the time-points specified using the same imaging modality used at baseline, irrespective of study treatment interruption or actual dosing (see [Table 7-1](#)). Imaging assessments for response evaluation will be performed every 8 weeks ( $\pm$  7 days) after randomization. Tumor assessments are to be performed every 12 weeks after primary analysis data cut-off and as clinically indicated, until disease progression.

Additional imaging assessments may be performed at any time during the study at the investigator's discretion to support the efficacy evaluations for a subject, as necessary. Clinical suspicion of disease progression at any time requires a physical examination and imaging assessments to be performed promptly rather than waiting for the next scheduled imaging assessment.

Each lesion that is measured at baseline must be measured by the same method (either same imaging method or by photography, including a metric ruler) and when possible, the same local radiologist/physician throughout the study so that the comparison is consistent. If an off-schedule imaging assessment is performed because progression is suspected, subsequent imaging assessments should be performed in accordance with the original imaging schedule.

Combined PET/CT may be used only if the CT is of similar diagnostic quality as a CT performed without PET, including the utilization of IV contrast media. At the discretion of the Investigators, FDG-PET scans may be performed to document progressive disease per RECIST 1.1 ([Appendix 1](#)).

All study imaging (including any off-schedule imaging studies) should be submitted to the designated imaging CRO for quality control and central review.

